## **Covariates**

We will include sex, age, cohabitation, education, employment, co-morbidity due to a tobacco-related disease and country of residence as covariates in the study. The covariates will be defined as follows:

### 1. Sex

Sex will be categorized as male (= 1), female (= 2).

### 2. Age

We will use age as a continuous variable (in years).

### 3. Cohabitation

We will define cohabitation as living alone (=1) or living with others (= 2).

### 4. Education

We will categorize education into three groups: Less than high school (= 1), high school (= 2), and university (= 3).

### 5. Employment

We will categorize current employment status as: no current employment, student or retired (= 1), currently part-time or full-time employed (= 2). This information is available in Sweden and Norway.

### 6. Comorbidity due to any tobacco-related disease

We will define any comorbidity due to a tobacco-related disease as: No tobacco-related comorbidity (= 1), any tobacco-related comorbidity (= 2). This information is available in Sweden and Norway.

### 7. Country

We will create a categorical variable with the country of residence as follows: Sweden (= 1), Norway (= 2), Finland (=3).

***Date variables***

1. *Year of latest assessment of cigarette smoking*

Format: YYYY

2. *Year of latest assessment of snus use*

Format: YYYY

3. *Date of COVID-19 Diagnosis*

Format: DD/MM/YYYY

4. *Date of Hospital Admissions due to COVID-19*

Format: DD/MM/YYYY

5. *Date of Intensive Care Admission due to COVID-19*

Format: DD/MM/YYYY

6. *Date of hospital discharge*

Format: DD/MM/YYYY

### **Statistical analysis**

Risk ratios (RR) and their corresponding 95% CI for COVID-19 infection, hospitalization, ICU, or death due to COVID-19 will be estimated through generalized linear models (GLM). We will use the Poisson family with robust standard errors and the maximum likelihood optimization algorithm to estimate the relative risk of a confirmed COVID-19 case, hospital admission, ICU, or death due to COVID-19 (Zou, 2004). First, adjusted Poisson regression (Zou, 2004) will be applied to assess the influence of exposure (smoking or snus) on the study's outcomes. If we assume that  $y_{ij}$  is the observed binary outcome (COVID-19 infection, hospital admission, ICU, or death due to COVID-19) for subject  $i$  in country  $j$ , the specification and the equation of the Poisson model is as follows:

$$\log(p_{ij}) = \beta_0 + \beta_1 X_{1ij} + \sum_k^R \beta_k X_{ijk} \quad (1)$$

where  $p_{ij}$  is the probability of the outcome  $y_{ij}$ ,  $X_{1ij}$  is the exposure (smoking/snus),  $\beta_0$  is the intercept,  $\beta_1$  is the regression coefficient corresponding to the exposure,  $X_{ijk}$  represents the subject's values of  $R$  covariates, and  $\beta_k$  is a regression coefficient corresponding to each covariate. Exponentiating  $\beta_1$  gives the corresponding relative risk, RR.

We will then apply a multilevel regression (Goldstein, 1995) which assumes that each country has its own COVID-19 infection probability, and this varies from one country to another. This will be the primary analytical model. In this multilevel model, the Poisson regression for COVID-19 infection will include an additional term  $u_j$ , which is the country-level random effects as a predictor variable:

$$\log(p_{ij}) = \beta_0 + \beta_1 X_{1ij} + \sum_k^R \beta_k X_{ijk} + u_j \quad (2)$$

In this model, the probability depends on the value of the random effects  $u_j$  which is the totality of unmeasured country-level variables that predict COVID-19 infection and are uncorrelated with the individual variables in the model.

As a secondary analysis, we will use a negative binomial count model (Hilbe, 2011, 2014) to assess inpatient length of stay (i.e. the cumulative number of days of hospitalization) as a measure of disease severity among tobacco users compared to non-tobacco users.

We will carry out stratified analyses by sex, age, education, and time period.

We will carry out three sensitivity analyses. First, we will analyse the data adding tobacco-related comorbidity and employment as additional confounders with data from Sweden and Norway. Second, we will analyse only data prospectively collected to explore the influence of information bias. For this purpose, we will include data from Sweden and Finnish data from 2018 and 2019. This data will be analyzed with Cox proportional hazards models with the same specifications as the primary analysis. We will use time in study as the timescale. Participants will be censored due to end of follow-up or the occurrence of the event.

Third, for death of COVID-19, we will also include a competing risk analysis to take right-censoring due to a death non-attributable to COVID-19 into account. Competing risk means that a subject can experience one of a set of different events during the study period. Accordingly, the use of traditional methods of survival analysis, such as the Kaplan-Meier survival function, will result in incidence estimates that are biased upward, irrespective of the independence between the competing events (Austin et al., 2016; Berry et al., 2010; Kim, 2007; Southern et al., 2006). Instead, we will use two models to fit a regression in the presence of competing risk, the cause-specific hazard modeling and the sub-distribution hazard modeling (Austin et al., 2016). The cause-specific hazard function implies the instant rate of occurrence of a specific event in subjects who have not experienced yet any of the different types of events (Andersen et al., 2002; Austin et al., 2016). If we consider two types of events, death due to COVID-19 causes and death due to non-COVID-19 causes, then the cause-specific hazard of COVID-19 death implies the instant rate of COVID-19 death in subjects who have not yet experienced

either event (Austin et al., 2016). In the cause-specific hazards regression model, we will model the effect of covariates by using the traditional Cox proportional hazards model after censoring individuals with competing events at the time of their occurrence.

Unlike the cause-specific hazard function, the revised risk set in the sub-distribution hazard function (Fine & Gray, 1999), also known as the cumulative incidence function regression model, allows to include subjects who are event-free and subjects who already experienced a competing event. In the sub-distribution hazard function, we will model the effect of covariates by using a proportional hazards model through the cumulative incidence function that allows for the estimation of the incidence of the occurrence of an event while taking competing risks into consideration (Austin et al., 2016; Fine & Gray, 1999).

All analyses will be conducted with STATA®, version 17 (StataCorp LP, College Station, Texas, USA) and R version 4.1.2. We will incorporate the complex sampling design in Finland in all analyses.

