## **Data Sources**

We will pool data from three Nordic countries, Sweden, Finland, and Norway. Briefly, Swedish data comes from a historical cohort of 424,386 clients of public dental clinics aged 23 and older in the Stockholm region with inception between October 2015 and January 2020, with follow-up from February 2020 to December 2020. In Sweden, the public dental clinics (Folktandvården, FTV) provide routine preventive visits (oral check-ups) to all residents who choose to receive care in these clinics. At each health check-up smoking and snus use are ascertained as past use, current use, and amount of current use. The national personal numbers assigned to every resident in Sweden at birth or at immigration will be used to obtain information on diagnoses of COVID-19 and of other diseases through record-linkage with regional health care registers. Demographic information will be extracted through record-linkage with the register of the total population of the Stockholm region held by Statistics Sweden.

The Finnish data will come from three pooled cross-sectional national health surveys in Finland (FinSote 2018-2020) of 44,199 participants aged 20 and older. The study samples included permanent residents in Finland from the FinSote surveys 2018, 2019, and 2020. The unique personal identifier assigned to all Finnish residents will be linked to the Communicable Diseases Registry to obtain information on diagnoses of COVID-19, to the Care Register for Health Care (HILMO) to obtain information on hospital admissions due to COVID-19, and to Statistics Finland Mortality Data to obtain information on deaths. Data on some sociodemographic characteristics will be also obtained from the Digital and Population Data Services Agency.

The Norwegian data will be based on the Norwegian Mother, Father and Child Cohort Study (MoBa) ([name] et al., 2016), and the Norwegian Influenza Pregnancy Cohort (NorFlu) (Laake, 2018), with linkages to the Norwegian Surveillance System for Communicable Diseases (MSIS), the Norwegian Immunisation Registry (SYSVAK), and the Norwegian Population Registry. MoBa is a nation-wide population-based cohort consisting of 280 000 participants, where

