parents were recruited during pregnancy from 1999 to 2008, while NorFlu is a pregnancy cohort consisting of 9 000 participants recruited in Oslo and Bergen during the swine flu pandemic in 2009-2010. Since March 2020, cohort participants have been regularly invited to answer electronic questionnaires. In June 2020 and January 2021, participants were asked to report current smoking. Questions about snus and other tobacco use were asked in January 2021 only. COVID-19 diagnoses are obtained from registry data (MSIS) based on PCR confirmed SARS-CoV-2 infection. Demographic information is extracted from the registries via linkage to the existing cohort databases. For the purpose of this study, all subjects who died before the onset of the pandemic (February 2020) in the three countries will be excluded from the analysis.

We developed a harmonization protocol to create a comparable dataset. The harmonization process started with identifying all possible variables to be used in the pooled analyses. We then identified common variables across countries, and only variables available in at least 2 countries will be included in the pooled analysis. Each country provided the format on which these variables were stored in their respective datasets. Finally, we elaborated a document describing the format for the harmonized variables. The principle of harmonization was to create variables with a minimum common format. The harmonized variables list is as follows:

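### The robust errors name no cluster unit although MoBa enrolled both parents, so the infection CIs are likely slightly too narrow if partners resemble each other in both tobacco use and infection

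*Combined protocol and SAP*

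**What the plan says.** The Statistical analysis section plans "Risk ratios (RR) and their corresponding 95% CI for COVID-19 infection, hospitalization, ICU, or death due to COVID-19". The variance method is given as "We will use the Poisson family with robust standard errors and the maximum likelihood optimization algorithm", with the modified Poisson method for binary data as its reference. No cluster unit is named. Model (2) adds one term, u_j, "which is the country-level random effects as a predictor variable", and of this model the plan says "This will be the primary analytical model". Country has three levels (Covariates, item 7).

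Under Data Sources, MoBa is a mother, father and child cohort of 280,000 in which "parents were recruited during pregnancy from 1999 to 2008". Both members of a couple can therefore be in the analysis. The harmonised variables include no family or household key. Cohabitation (Covariates, item 3) is a living-alone indicator. As a covariate it shifts a person's expected risk but does not link two people in one home. The only sampling or dependence feature carried into the analyses is the Finnish complex design, in the last sentence of the analysis text.

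**The concern.** The sandwich variance in modified Poisson regression repairs the mismatch between a Poisson variance and a binary outcome. Unless a cluster is declared, it does so person by person. A country intercept absorbs differences between countries, not the resemblance of two people who share a home. SARS-CoV-2 spreads within households, and partners may share tobacco habits. When outcome and exposure are both positively correlated within pairs, standard errors that treat persons as independent are too small, and the intervals for the infection RRs claim somewhat more precision than the data hold. The study is justified partly by greater precision on a disputed association, so its intervals should be right.

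**Working it through.** The plan states no sample size, power, event count or design effect, so there is no planned figure to reproduce.

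**Inputs from Data Sources.** Sweden 424,386; Finland 44,199; MoBa 280,000; NorFlu 9,000. The total is 757,585, so MoBa's share by enrolment is w = 280,000 / 757,585 = 37.0%.

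**Assumed inputs (not in the documents).**
- ρ_y, within-couple correlation of infection: 0.1 to 0.5.
- ρ_x, within-couple correlation of exposure: 0.2 to 0.6, with 0 and −0.1 as checks.
- c, share of MoBa members whose partner is also analysed: 0.3 to 1.0.

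**Formulas.** For an individual-level exposure and clusters of two:
- MoBa design effect: DEFF = 1 + c·ρ_y·ρ_x.
- Pooled design effect, weighting MoBa by enrolment and counting no other pairs: 1 + w·c·ρ_y·ρ_x.
- Required SE ÷ person-level robust SE = √DEFF.
- Actual coverage of a nominal 95% CI = 2Φ(1.96/√DEFF) − 1.

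**Results with all MoBa members paired (c = 1).**

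| ρ_y | ρ_x | MoBa SE factor | MoBa coverage | Pooled SE factor | Pooled coverage |
|---|---|---|---|---|---|
| 0.1 | 0.2 | √1.020 = 1.010 | 94.8% | √1.007 = 1.004 | 94.9% |
| 0.3 | 0.4 | √1.120 = 1.058 | 93.6% | √1.044 = 1.022 | 94.5% |
| 0.5 | 0.6 | √1.300 = 1.140 | 91.4% | √1.111 = 1.054 | 93.7% |
| 0.3 | 0 | 1.000 | 95.0% | 1.000 | 95.0% |
| 0.3 | −0.1 | √0.970 = 0.985 | 95.3% | √0.989 = 0.994 | 95.1% |

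**Fewer pairs.** At (0.3, 0.4), c = 0.3 gives a factor of 1.018 in MoBa and 1.007 pooled; c = 0.6 gives 1.035 and 1.013. The low end of the positive range, c = 0.3 at (0.1, 0.2), gives 1.003 and 1.001.

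**Simulation check.** Settings: 20,000 couples, 2% infected, 10% smokers, true RR 1, 1,500 replicates, no covariates. The Monte Carlo error of a coverage figure is √(0.95 × 0.05 / 1,500) = 0.6 percentage points.
- At (0.3, 0.4), couple-clustered over person-robust SE is 0.1235 / 0.1169 = 1.056 (formula 1.058). Coverage is 93.7% with person-level errors and 95.1% with clustering.
- At (0.5, 0.6) the ratio is 0.1338 / 0.1174 = 1.140 (formula 1.140). Coverage is 91.4% and 94.9%.
- At ρ_x = 0 the two errors agree and coverage is about 95%.

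**What this does to an interval.** Take an illustrative RR of 0.80 with upper limit 0.910, so ln(0.910/0.80) = 0.1288. A factor of 1.013 gives 0.1305 and an upper limit of 0.912. A factor of 1.054 gives 0.1358 and 0.916.

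**The case against.** A reader might infer that the primary CIs are certainly too narrow, and by as much as in the all-paired MoBa rows. The documents do not support that. They give neither correlation, nor the number of couples analysed, nor whether parents recruited in 1999 to 2008 still lived together in 2020. With uncorrelated exposure nothing changes, and with negative correlation the unclustered interval is slightly too wide. The primary estimate pools three countries, and MoBa's analysed share may be below 37% because its tobacco data come from questionnaires in June 2020 and January 2021. The models also adjust for age, education and cohabitation, on which partners may be alike, so the correlation left after adjustment may be smaller than the raw one. All of this stands, and it limits the size.

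A reader might also infer that the Swedish cohort adds many cohabiting pairs. It may, but Data Sources describes individual dental clients and mentions no household link.

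Nor does the argument reach every analysis. The Cox sensitivity analysis uses only Swedish and Finnish data, and the competing-risk analysis concerns death. Sex-stratified analyses place mother and father in separate strata. Whether one person can appear twice across cohorts or surveys is a separate question that this point does not settle.

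Finally, robust errors in the multilevel model might be clustered on country by the software. Households lie within countries, so their dependence would be nominally covered, but a robust variance from three clusters is unreliable. This reading does not rescue the plan; it shows that the cluster unit has to be stated.

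**Conclusion.** The point holds as a modest one. As written, the plan makes no provision for dependence between partners, although one of its largest cohorts enrolled couples and the outcome is contagious. If infection and tobacco use are both positively correlated within couples, which is plausible but undocumented, the CIs for the infection RRs are likely slightly too narrow. Over the assumed ranges the required SE is 0.1 to 5.4% larger than the person-level robust SE in the pooled estimate, and about 1% larger at correlations 0.3 and 0.4 with 30 to 60% of MoBa paired. In MoBa alone it is 0.3 to 14% larger, the top figure needing every member paired and correlations of 0.5 and 0.6. Pooled coverage stays between 93.7% and 95%. The pooled figures weight by enrolment and count MoBa pairs only.

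**What to change.** For the infection models, state the cluster unit and use cluster-robust errors on the MoBa family link, with everyone who has no linked partner as a cluster of one. Add a Swedish household key only if the register linkage supplies it. Enter country as two fixed indicators in place of u_j, so that clustering below country is possible; country is already a listed covariate. This changes the declared primary model and should be recorded as such. With cohorts this large the exposure RR should move little, and model (2) can be kept as a supporting analysis.

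If the family link cannot be added to the pooled file, run a sensitivity analysis that keeps one parent per family.

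The cost is one more key in the harmonised file and slightly wider intervals. The one-parent alternative also loses the records of the parents left out.

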## **Outcome Variables**

The study will include five outcomes: any diagnosis of COVID-19, hospital admission for COVID-19, length of hospital stay for COVID-19; intensive care use due to COVID-19, and death attributable to COVID-19. The follow-up period for all outcomes was from February 2020 until December 2020.

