## *4. Death for COVID-19*

Death due to COVID-19 will be established using the Swedish, Finnish, and Norwegian Cause of Death Registries. All deaths occurring during the follow-up period with COVID-19 registered as the main cause will be included. The restriction to main cause will be done to maximize the specificity of the diagnosis (Ioannidis, 2021). A categorical variable for death due to COVID-19 will be created (Alive at the end of follow-up= 1, Death during follow-up= 2).

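### Length of stay is read as disease severity, but the plan has no rule for in-hospital death or open stays, so the stay ratio confuses early death with early recovery

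*Combined protocol and SAP*

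**What the plan says.** The Outcome Variables section names five outcomes. The list ends with "length of hospital stay for COVID-19; intensive care use due to COVID-19, and death attributable to COVID-19". The numbered definitions that follow cover the other four; length of stay has none.

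Its only specification is in the Statistical analysis section: "As a secondary analysis, we will use a negative binomial count model" for inpatient stay, described as "i.e. the cumulative number of days of hospitalization) as a measure of disease severity among tobacco users compared to non-tobacco users".

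The observation window is common to all outcomes: "The follow-up period for all outcomes was from February 2020 until December 2020". The Date variables list contains "Date of hospital discharge" but no date of death and no indicator of discharge alive or dead.

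Competing-risk methods are planned for one outcome: "Third, for death of COVID-19, we will also include a competing risk analysis to take right-censoring due to a death non-attributable to COVID-19 into account". Cause-specific and sub-distribution models are both described for that purpose. Death is otherwise a separate binary outcome, restricted by registered cause: "All deaths occurring during the follow-up period with COVID-19 registered as the main cause will be included".

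No section says how an in-hospital death enters the day count, how a stay still open at the end of follow-up is scored, or whether the model covers admitted patients only or the whole cohort with zeros.

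**The concern.** A count of hospital days measures severity only if more days mean worse disease. Death breaks that link. A patient who dies on day 3 has accrued 3 days, the same as a patient who recovers and goes home on day 3, and fewer than a survivor discharged on day 10. Unless a rule says otherwise, the model cannot tell the first two apart.

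The plan explains at length why competing deaths need special methods for COVID-19 mortality. It does not carry that reasoning over to the outcome whose measurement death cuts short.

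What is at stake is the reading of one secondary result. If tobacco users die in hospital more often and early, their mean stay can shorten, and a ratio below 1 labelled as severity would suggest milder disease. The Background warns against biased protective findings on tobacco. The sources of bias it names are selection and confounding; this would be a different one, with a similar consequence for readers.

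**Working it through.** The plan gives no length-of-stay, in-hospital mortality or power figure, so there is nothing to reproduce. All inputs below are assumptions.

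**Inputs**
- d: in-hospital mortality in the unexposed, 5% to 20%.
- k: death hazard ratio, exposed v unexposed, 1.5 or 2.
- s: live-discharge hazard ratio, 1 (no effect) or 0.9 (discharge slowed by 10%).
- Hazards are constant over the stay.

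**Formula, admitted patients.** Scale the total hazard in the unexposed to 1, so the discharge hazard is 1 − d and the death hazard is d. Mean stay is 1 divided by the total hazard. Therefore:

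mean-stay ratio = 1 / [s(1 − d) + kd]

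mortality in the exposed = kd / [s(1 − d) + kd]

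**Results for k = 1.5**

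| d | s = 1 | s = 0.9 |
|---|---|---|
| 5% | 1/1.025 = 0.98 | 1/0.930 = 1.08 |
| 10% | 1/1.050 = 0.95 | 1/0.960 = 1.04 |
| 15% | 1/1.075 = 0.93 | 1/0.990 = 1.01 |
| 20% | 1/1.100 = 0.91 | 1/1.020 = 0.98 |

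At d = 15% and s = 1, mortality in the exposed is 0.225/1.075 = 21% against 15%, yet stays look 7% shorter.

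The s = 0.9 column needs a reference. With slower discharge and no effect on death (k = 1), the ratio at d = 15% would be 1/(0.765 + 0.15) = 1.09. Raising the death hazard brings it down to 1.01. So even where the ratio stays above 1, added lethality makes the exposed look less ill.

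**Results for k = 2.** With s = 1, the ratio is 1/1.05 = 0.95, 1/1.10 = 0.91, 1/1.15 = 0.87 and 1/1.20 = 0.83 at d = 5%, 10%, 15% and 20%. With s = 0.9, it is 1/1.01 = 0.99 at 10% and 1/1.12 = 0.89 at 20%. A negative binomial model fitted to simulated whole-day stays (d = 20%, k = 2, s = 1) gives 0.85, close to the closed form.

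**When deaths occur.** Drop constant hazards. Let survivors stay 10 days on average and fatal stays average D days, and let mortality double from p to 2p:

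ratio = [10(1 − 2p) + 2pD] / [10(1 − p) + pD]

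- D = 3: 8.6/9.3 = 0.93 at p = 10%; 7.2/8.6 = 0.84 at p = 20%.
- D = 10: 1.00 at both.
- D = 15: 11.0/10.5 = 1.05 at p = 10%; 12.0/11.0 = 1.09 at p = 20%.

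The direction therefore depends on whether fatal stays are shorter or longer than survivors' stays.

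**Whole-cohort reading.** If people never admitted enter as zeros, the ratio of mean days is the admission risk ratio times the ratio among the admitted. With 0.91 among the admitted (d = 10%, k = 2, s = 1), an assumed admission risk ratio of 1.2 gives 1.2 × 0.91 = 1.09, and 0.8 gives 0.8 × 0.91 = 0.73. Truncation by death still enters, but admission risk can hide or exaggerate it.

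**The case against.** The plan nowhere writes that death counts as a short stay, or that open stays are treated as complete. A reader might infer such rules, but the documents are silent. The confusion follows from the definition of the measure and the absence of any rule.

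A reader might also infer that the model will make tobacco look protective. The documents do not support that. They give no mortality, no stay lengths and no timing of deaths. An exposure that worsens disease could well slow recovery too, and then most of the ratios for k = 1.5 exceed 1. Long fatal stays reverse the bias. On the whole-cohort reading, the ratios for admitted patients are not what the model estimates.

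Two further criticisms are weak. First, an ordinary negative binomial would be misspecified if admitted patients always had at least one day, but discharge date minus admission date can be zero, and the plan states no counting convention. Where truncation does apply, the effect is small. For means of 10 and 12 days (true ratio 1.2), the means among positive counts are 10.29 and 12.25 at dispersion 0.5 (ratio 1.19), and 11 and 13 at dispersion 1 (ratio 1.18). Second, cutting stays at the end of follow-up has not been quantified, and there is no stated reason for it to differ by tobacco use.

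The analysis is secondary, and ICU care and COVID-19 death are separate outcomes, so a difference in lethality would largely show there. This stands in part. The death outcome counts only deaths with COVID-19 as main cause, whereas any in-hospital death ends a stay, and nothing in the plan ties the two results together. Dates of death are implied by the planned competing-risk analysis, so their absence from the date list is a listing gap.

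Finally, replacing cumulative days would change the estimand, since cumulative days include readmissions, and restricting to admitted patients conditions on something tobacco may affect. Both points stand and shape the fix.

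**Conclusion.** The concern holds in this form: as specified, the stay ratio is not a clean measure of severity, because it cannot separate early death from early recovery. This is more than missing detail, since following the plan as written produces that confusion.

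Neither size nor direction can be fixed from the documents. Under constant hazards with k = 1.5, the ratio among admitted patients lies between 0.98 and 0.91 if discharge is unaffected, and between 1.08 and 0.98 if discharge is slowed by 10%, for in-hospital mortality of 5% to 20%. It moves the other way if fatal stays outlast survivors' stays. The supportable statement is that a more lethal exposure can look milder, not that it will. The primary model and the binary outcomes are unaffected.

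**What to change.** 1. State whether the length-of-stay model covers admitted patients or the whole cohort with zeros, how days are counted, and how in-hospital deaths and open stays enter.
2. Among admitted patients, add an analysis of time from first COVID-19 admission to live discharge, with in-hospital death from any cause as a competing event and open stays censored at the end of follow-up. Use the cause-specific and sub-distribution models already planned for COVID-19 death. In the worked case with d = 15%, k = 1.5 and s = 1, live discharge falls from 85% to 79%, so the sub-distribution result would point towards harm where the stay ratio of 0.93 points away.
3. Report in-hospital death by exposure beside it, and do not interpret the stay ratio alone as severity.
4. Keep cumulative days as a descriptive secondary measure.
5. Add date of death to the Date variables list.

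The cost is SAP wording, one more variable in the harmonized list and one further competing-risk analysis. The severity reading becomes a discharge hazard ratio, which is less intuitive than a ratio of days, and readmissions must be reported separately. The added analysis conditions on admission, which tobacco use may influence; state this as a limitation. Silently excluding deaths would not be a remedy, because it conditions on survival.

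### The first sensitivity analysis drops Finland and adds employment and tobacco-related comorbidity in one step, with no reference model on the same records, so its result cannot be attributed to any one change

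*Combined protocol and SAP*

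**What the plan says.** Under Statistical analysis, the multilevel Poisson model with a country random effect is named as the main one: "This will be the primary analytical model". Three sensitivity analyses follow. The first is "First, we will analyse the data adding tobacco-related comorbidity and employment as additional confounders with data from Sweden and Norway".

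The Covariates section explains why Finland is left out. Employment is coded as "no current employment, student or retired (= 1), currently part-time or full-time employed (= 2). This information is available in Sweden and Norway", and comorbidity as "No tobacco-related comorbidity (= 1), any tobacco-related comorbidity (= 2). This information is available in Sweden and Norway". The comorbidity item gives no disease list, no look-back period and no timing relative to the tobacco assessment.

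Two other statements bear on which covariates the primary model contains. The Covariates section opens with "We will include sex, age, cohabitation, education, employment, co-morbidity due to a tobacco-related disease and country of residence as covariates in the study", and Data Sources sets the rule that "only variables available in at least 2 countries will be included in the pooled analysis". Both would admit employment and comorbidity to the pooled analysis, whereas the sensitivity analysis treats them as additions to it.

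The plan does not refit the primary covariate set to Sweden and Norway alone, does not enter the covariates one at a time, and gives no rule for reading a change in the RR. It does not mention mediation. The other two sensitivity analyses (prospectively collected data with Cox models, and competing risks for death) address different questions.

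**The concern.** A sensitivity analysis is informative when one thing changes and the rest is held fixed. Here three things change together: the population, adjustment for employment, and adjustment for tobacco-related disease. Their effects on the RR can differ in sign, so agreement with the primary RR is as hard to interpret as disagreement.

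The label adds to the problem. A disease variable selected for being tobacco-related may in part be caused by smoking. Where it is, and where it also raises the risk of admission, intensive care or death, adjusting for it removes part of the effect of smoking. A reader told that both variables are confounders would naturally take any attenuation as confounding removed. The Background section says that the role of tobacco in these severe outcomes is unresolved and warns about the public health consequences of biased findings, so that misreading would matter here.

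**Working it through.** The plan states no numerical result for this analysis, so there is none to reproduce. The main point comes from reading the text. The arithmetic below shows only how large each component could be.

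**The two models side by side**
- Primary: Sweden, Norway and Finland, with a covariate set that is not stated unambiguously.
- Sensitivity 1: Sweden and Norway, with employment and comorbidity added.
- Missing link: the primary covariates fitted to the Sweden and Norway records used in sensitivity 1.

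**Inputs from the documents (Data Sources).** Sweden 424,386; Finland 44,199; Norway 280,000 + 9,000 = 289,000 recruited. The number in Norway who answered the tobacco questions is not given. All other inputs below are assumptions.

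**1. Dropping Finland**
- Share of all enrolled: 44,199 / (424,386 + 44,199 + 289,000) = 44,199 / 757,585 = 5.8%.
- Share if Norway contributes nothing: 44,199 / 468,585 = 9.4%.
- Take the pooled log RR as a weighted mean of the Finnish log RR and the log RR elsewhere. Dropping Finland then multiplies the pooled RR by exp(−share × ln(ratio)), where ratio is the Finnish RR divided by the RR elsewhere.
- Ratio 0.67: 1.024 at 5.8% and 1.038 at 9.4%.
- Ratio 1.25: 0.987 at 5.8% and 0.979 at 9.4%.
- The shift is therefore about 1–4%. These weights are headcounts, not events or statistical information, so this is not a bound. With an assumed weight of 20%, an RR of 0.80 elsewhere and a Finnish RR of 0.67 to 1.30, the pooled RR is 0.772 to 0.882.

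**2. Comorbidity as a pure mediator with no direct effect.** Let p1 and p0 be the comorbidity prevalence in current and non-current smokers, and r the outcome RR for comorbidity. Total RR = (1 + p1(r − 1)) / (1 + p0(r − 1)), and the adjusted RR is 1.00 by construction.
- p0 = 10%, p1 = 15%, r = 2: 1.15 / 1.10 = 1.05.
- p0 = 10%, p1 = 20%, r = 2: 1.20 / 1.10 = 1.09.
- p0 = 10%, p1 = 20%, r = 3: 1.40 / 1.20 = 1.17.
- p0 = 10%, p1 = 30%, r = 3: 1.60 / 1.20 = 1.33.

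**3. Comorbidity as a confounder, in the opposite direction.** If illness prompts quitting, so that prevalence is 10% in current and 15% in non-current smokers, the same formula with r = 2 gives 1.10 / 1.15 = 0.96. Adjustment would then correctly remove an apparent protection.

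**4. Employment as a pure confounder.** Use the same formula with employment prevalence and the outcome RR for employment.
- 60% of smokers and 70% of non-smokers employed, RR 1.2: unadjusted/adjusted = 1.12 / 1.14 = 0.982.
- 50% and 70%, RR 2: 1.50 / 1.70 = 0.882.
- Adjustment therefore raises the RR by about 2% (1 / 0.982) to 13% (1 / 0.882).

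**5. Cancellation.** Take the second case in step 2: adjustment multiplies the RR by 1.10 / 1.20 = 0.917. Take employment at 50% and 70% with RR 1.5: adjustment multiplies it by 1.35 / 1.25 = 1.08. If the two act independently, the product is 0.917 × 1.08 = 0.99. Multiplying by 1.024 for Finland gives 1.01. Three shifts of about −8%, +8% and +2% would look like a robust result.

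**The case against.** The strongest reply is that the plan's label may be right. The exposure contrast is current against non-current smoking, so the reference group includes former smokers. In Norway, smoking was reported in June 2020 and January 2021, so earlier disease could have changed smoking status. Comorbidity would then confound this contrast, as step 3 shows. This stands: a reader might infer that comorbidity is an established mediator, but with no disease list and no timing the documents do not support that. The mediation argument is also weaker for infection and for snus. The mixed role is a reason to enter comorbidity as a separate step.

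A reader might also infer that a harmful total effect would disappear from the report, or that the analysis was designed to test unmeasured confounding. The documents support neither. On the reading that the primary model omits these two covariates, its RR is still reported. The plan states no purpose for this analysis beyond the label, and both added variables are measured.

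It is also fair to say that Finland's exclusion is forced by data availability, is openly stated, and is probably the smallest of the three changes for infection. It could weigh more for admission and intensive care, because the Norwegian linkages listed in Data Sources name no hospital register.

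Finally, employment need not be a pure confounder. Its first category combines people without work, students and retired people, and tobacco-related illness may itself affect employment. The step that adds employment therefore cannot serve as the full test of confounding. None of these replies supplies the missing reference model.

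**Conclusion.** The concern holds as a defect of attribution and labelling in a sensitivity analysis. As specified, neither a difference from the three-country primary RR nor agreement with it can be assigned to the change of population, to employment or to comorbidity. This conclusion rests on the text alone and needs no assumed figure.

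Whether comorbidity acts mainly as mediator or as confounder is not settled by the documents, so presenting it simply as a confounder is not justified. The case for partial mediation is strongest for smoking with admission, intensive care and death. The figures of about 1–4% for Finland, 1.05–1.33 falling to 1.00 for mediation, and 2–13% for employment are illustrations under assumed inputs, not estimates for this study.

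The primary estimate is unaffected, provided that employment and comorbidity are outside the primary model, which the plan should say. The change should be made because it makes an analysis already planned interpretable at very little cost.

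**What to change.** On identical Sweden-plus-Norway records with complete covariates, fit four models for each exposure and outcome: (a) the primary covariates, (b) plus employment, (c) plus comorbidity, (d) both. Then:

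- Read the effect of adding covariates only against (a).
- Read the effect of dropping Finland, together with any records lost to missing covariates, from the primary model against (a).
- Describe (c) and (d) as adjusted for a possible mediator as well as a possible confounder, not as better-adjusted total effects. Do not treat the step from (a) to (b) as the complete test of confounding.
- State that employment and comorbidity are not in the primary model, and reconcile this with the opening of the Covariates section and the two-country rule in Data Sources.
- Define the diseases that count as tobacco-related and state when they are ascertained relative to the tobacco assessment and the start of follow-up.

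Model (d) is already planned, so the cost is three extra fits per exposure–outcome pair. With three exposures and five binary outcomes (diagnosis, two admission definitions, intensive care, death) that is up to 3 × 3 × 5 = 45 fits, more if cigarette amount is run in both its codings. They can be run in a loop. No new data are needed, and the text change is a few sentences.
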